LIST OF ABBREVIATIONS AND RELEVANT DEFINITIONS

AAS	Flameless atomic absorption spectrometry
AE	Adverse Event
ALT	Alanine transaminase
AR	Adverse reaction
AST	Aspartate transaminase
AUC	Area Under the Curve
C _{max}	Maximum observed plasma concentration after single dose administration
CRF	Case report form
CTCAE	Common Terminology Criteria for Adverse Events
HIPEC	hyperthermic intraperitoneal chemotherapy
IEC	Independent Ethics Committee
ICP-OES	inductively coupled plasma optical emission spectrometry
IPCH	intra-operative intra-peritoneal chemo-hyperthermia
L	Liter
LDH	Lactate Dehydrogenase
MDRD	Modified Diet in Renal Disease
METC	Medical research ethics committee (in Dutch: Medisch Ethische Toetsing Commissie)
PC	peritoneal carcinomatosis
PI	Principal Investigator: a person responsible for the conduct of a clinical study at a study site. Every study centre has a principal investigator.
PK	Pharmacokinetics
Pt	Platinum
PUF	plasma ultrafiltrate
SAE	Serious Adverse Event
SAR	Serious Adverse Reaction
Sponsor	The sponsor is the party that commissions the organization or performance of the research, for example a pharmaceutical company, academic hospital, scientific organization or investigator. A party that provides funding for a study but does not commission it is not regarded as the sponsor, but referred to as a subsidizing party
SUSAR	Suspected Unexpected Serious Adverse Reaction
T _{1/2}	Half life time
T _{max}	Time to maximum observed plasma concentration after dose
UAR	Unexpected Adverse Reaction
UMCN	Radboud University Medical Center (in Dutch: Radboudumc)
WHO	World Health Organization
WMO	Medical Research Involving Human Subjects Act (in Dutch: Wet Medisch-wetenschappelijk Onderzoek met Mensen)

SUMMARY

Rationale

Cytoreductive surgery combined with hyperthermic intraperitoneal chemotherapy (HIPEC) is standard care in the treatment of patients with peritoneal carcinomatosis as a result of intra-abdominal cancers. Cytoreduction is a procedure that aims for the complete removal of all visible tumours affecting the protective lining of the abdomen. The cytoreductive procedure itself is complex and can last several hours. After the surgical procedure is completed, HIPEC is performed to attack non-visible tumour cells. The main goal of HIPEC is to obtain high local concentrations of the drug in the abdominal cavity with high penetration in tumour tissue, while avoiding systemic exposure. In many (inter)national centres oxaliplatin is used for the primary HIPEC treatment. The recommended dose of oxaliplatin is 460 mg/m^2 perfused for 30 minutes at 43°C in dextrose 5%, performed following the open 'coliseum' technique. This includes lifting the edges of the surgical wound upwards and suspending them under traction by threads, thus optimizing exposure of intra-abdominal viscera. The abdomen is filled with dextrose 5% and with a rollerpump the perfusate is circulated in the abdominal cavity. Although the oxaliplatin dose of 460 mg/m^2 is widely accepted, the exact procedure of HIPEC differs between institutions and surgeons. Platinum concentration in the perfusate at the beginning of HIPEC depends on both body surface area and the volume of the abdominal cavity. Due to a great variety in the volume of the abdominal cavity, platinum concentration in the perfusate might differ between patients. Moreover, there is no consensus about the usefulness of flushing the HIPEC system with crystalloids at the end of oxaliplatin administration. Flushing is predominantly performed with the idea to minimize both systemic exposure of ultrafilterable platinum and personnel exposure to platinum-contaminated exudate. On the other hand, HIPEC without flushing might increase effectiveness because intraperitoneal tumour cells are exposed to high concentrations of oxaliplatin for a longer time period. The option of flushing is based on an individual preference of the surgeon. Currently, there is a lack of knowledge on the effect of flushing on tumour platinum exposure, systemic platinum exposure and platinum concentration in drain exudate and thereby personal exposure. Therefore we want to perform a study to investigate the effect of flushing after HIPEC on tumour exposure, systemic exposure and on wound exudate concentration. The results of this study will provide answers about the effect of flushing the abdominal cavity after HIPEC procedure. If flushing has no effect on peritoneal tissue exposure but does decrease systemic exposure and/or platinum concentration in exudate, flushing should be recommended to decrease personnel exposure and systemic toxicity.

Objective

Primary objective:

1. To determine the effect of flushing after HIPEC on tissue platinum exposure

Secondary objectives:

1. To explore the effect of flushing after HIPEC on wound exudate platinum concentration
2. To explore the effect of flushing after HIPEC on systemic exposure of total and unbound platinum

3. To explore the relation between the platinum concentration in instillate on tissue platinum exposure
4. To explore the relation between the platinum concentration in instillate on systemic exposure of total and unbound platinum exposure
5. To explore the effect of the degree of cytoreduction on systemic total and unbound platinum exposure

Study design

Single-centre, prospective, open, pharmacokinetic (PK) cohort study.

Study population

Twenty patients with peritoneal carcinomatosis as a result of intra-abdominal cancers who are already planned for HIPEC treatment with oxaliplatin as part of routine clinical care will be included in the study.

Intervention

The first 10 patients will undergo HIPEC procedure with flushing afterwards (the current practice by Radboudumc), followed by 10 patients who will be treated with HIPEC without flushing afterwards (new Radboudumc protocol that will be implemented in the beginning of 2018). Peritoneal fluid, peritoneal tissue, blood and wound exudate samples will be collected in all patients on prespecified time points during and after the HIPEC procedure.

Main study parameters/endpoints:

The main study parameter is the change in tissue platinum exposure before and after flushing. Tissue platinum exposure is expressed in concentration platinum per milligram tissue (ng/mg).

Nature and extent of the burden and risks associated with participation, benefit and group relatedness

Patients who participate in the study will receive the standard treatment. Therefore, the risk for participation in this study is regarded negligible. Collection of peritoneal fluid, blood, and wound exudate samples do not put patients at risk or interfere with standard treatment. Three 5ml peritoneal fluid samples will be taken 10, 20 and 30 minutes after intraperitoneal administration of oxaliplatin. Wound exudate samples of 5 ml will be taken from drain bottles at the moment that they are changed until day three post-surgery. During and after HIPEC a total of thirteen blood samples of 10ml will be taken from a central venous catheter that is placed as routine care prior to cytoreductive surgery with HIPEC. In the group of patients receiving HIPEC with flushing two 5-cm diameter non-tumour peritoneal tissue samples will be taken prior to and at the end of flushing. In the group of patients receiving HIPEC without flushing one 5-cm diameter non-tumour peritoneal tissue sample will be taken prior to abdominal closure. Compared to the complexity and amount of cytoreduction that is performed during surgery this can be considered as a negligible additional tissue collection procedure.

Benefits associated with participating in this study are that patients and their treating physician get insight into the effect of flushing after HIPEC on tumour platinum exposure and that the HIPEC procedure can be optimized for future patients.

1. INTRODUCTION AND RATIONALE

Peritoneal carcinomatosis is generally considered to be an untreatable terminal disease with a median survival of 6 months with 5-FU-based chemotherapy(1) and 1 year with chemotherapy including oxaliplatin. Systemic chemotherapy provides limited benefit. The use of cytoreductive surgery followed by HIPEC for peritoneal carcinomatosis as a result of intra-abdominal cancers has shown great improvement of survival rates compared with standard palliative surgery and chemotherapy. Survival rates improved to a median of two years and 20% of patients live longer than five years after the treatment (2-6). Therefore cytoreductive surgery combined with HIPEC in the treatment of peritoneal carcinomatosis is progressing towards a new standard of care (7). Despite the success of the treatment, there is a lack of agreement on many issues concerning the cytotoxic drug, dose, duration, carrier solution and technique.

Although no comparative studies between different cytotoxic drugs have been performed, the experience that has been obtained with oxaliplatin is most encouraging. Therefore primary HIPEC procedure consists of intraperitoneal administration of oxaliplatin. The main goal of HIPEC is to obtain high local oxaliplatin concentrations in the abdominal cavity with high penetration in tumour tissue, while avoiding systemic exposure. The advantage of intraperitoneal administration is confirmed in several PK studies (8, 9). Administration of 5-FU significantly increases the antitumor activity of intravenous administered oxaliplatin in the treatment of colorectal cancer (10-12). HIPEC with oxaliplatin is preceded by intravenous administration of 5-fluorouracil ($400-450 \text{ mg/m}^2$) and folic acid (20 mg/m^2), to potentiate oxaliplatin efficacy in the tumour cells (9). 5-FU is distributed to peritoneal fluid and tumor nodules after intravenous administration during HIPEC (13).

In order to balance cytotoxic activity and risk of toxicity, which is related to systemic exposure, it is important to study the PK of oxaliplatin during the HIPEC procedure. Based on previous PK work the most efficient dose for administration of oxaliplatin during HIPEC has been defined (8, 9, 14-27). The recommended dose of oxaliplatin is 460 mg/m^2 perfused during 30 minutes at 43°C in dextrose 5% following the open 'coliseum' technique. The open 'coliseum' technique is chosen because previous experimental data suggest higher tissue penetration and a more homogenous distribution compared to the closed technique (28). Some studies suggest the use of a standard volume of instillate of 2 L/m^2 , leading to a fixed concentration of oxaliplatin in the peritoneal cavity (9). In the Radboud University Medical Centre the abdominal cavity of the patient is completely filled with dextrose 5% before oxaliplatin is administered, to ensure contact with the whole peritoneum, for which a volume up to 6 litres may be needed. Because the volume of the abdominal cavity differs largely between patients, there is a great variety of oxaliplatin concentration in the instillate and thereby in the abdominal cavity. Together with the duration of the procedure, oxaliplatin concentration in instillate is an important variable that might influence tumour penetration and systemic absorption (9, 16, 21). In addition to these variables tumour penetration can be influenced by several other pharmacokinetic and non-pharmacokinetic variables, including carrier solution, pressure, tumor nodule size, nodule density, vascularity and interstitial fluid pressure.

Although a national standardized drug dose for oxaliplatin during HIPEC (460mg/m²) is accepted, the exact procedure of HIPEC can differ between institutions and surgeons. There is no consensus about the usefulness of flushing the HIPEC system with crystalloids at the end of oxaliplatin administration. Flushing is predominantly applied with the idea to minimize both systemic exposure and personnel exposure. On the other hand, HIPEC without flushing might increase effectiveness because intraperitoneal tumour cells might be exposed to oxaliplatin for a longer time period. The option of flushing is based on individual preferences of the surgeon. There is no standardized procedure for flushing after HIPEC. If a surgeon decides to flush after HIPEC the volume and time of flushing differs between patients and between surgeons. There is a lack of knowledge on the effect of flushing on tumour tissue exposure, systemic exposure and wound exudate platinum concentration. Therefore we want to perform a study to investigate the effect of flushing after HIPEC on tissue exposure, systemic exposure and wound exudate platinum concentration. The results of this study will help to further optimise and standardize the HIPEC procedure.

2. OBJECTIVES

Primary objective:

1. To determine the effect of flushing after HIPEC on tissue platinum exposure

Secondary objectives:

2. To explore the effect of flushing after HIPEC on wound exudate platinum concentration
3. To explore the effect of flushing after HIPEC on systemic unbound platinum exposure
4. To explore the relation between the platinum concentration in instillate on total tissue platinum exposure
5. To explore the relation between the platinum concentration in instillate on systemic unbound platinum exposure
6. To explore the effect of the degree of cytoreduction on systemic unbound platinum exposure

3. STUDY DESIGN

Patients

Eligible patients for study entry include patients with a diagnosis of peritoneal carcinomatosis as a result of intra-abdominal cancers who are already planned for HIPEC treatment with oxaliplatin as part of routine clinical care. To determine the effect of flushing after HIPEC on tissue exposure (primary objective) a group of 10 patients are needed who undergo HIPEC with flushing afterwards. To explore the differences of flushing vs. non-flushing (secondary objectives) 10 more patients are needed who undergo HIPEC without flushing afterwards. Cytoreductive surgery and HIPEC will be performed according to the standard local procedure.

Flushing

Flushing after HIPEC will be performed in the first 10 patients. Flushing will be performed immediately after evacuation of the instillate. In this study the abdominal cavity will be flushed during 5 minutes with 2L/m² of sodium chloride 0.9%.

PCI score

To explore the effect of the degree of cytoreduction on systemic exposure of unbound platinum it is necessary to objectively classify the extensiveness of the peritoneal cancer and thereby the intensity of the surgical intervention. As part of routine work the peritoneal cancer index (PCI) is assessed prior to cytoreduction.

CC-score

To completeness of cytoreduction score (CC-Score), as described by Jacquet et al (29), is used to score the completeness of the surgery. A CC-0 score indicates that no macroscopic peritoneal tumour remains after cytoreduction, a CC-1 score indicates that persisting tumour nodules are < 2.5 mm, a CC-2 score indicates residual tumour nodules between 2.5 mm and 2.5 cm and a CC-3 score indicates tumour nodules > 2.5 cm or a confluence of unresected tumour. All patients who do not achieve a CC-0 score will be excluded.

Peritoneal tissue samples

Two 5-cm diameter non-tumour peritoneal tissue samples will be taken from all patients that underwent HIPEC with flushing afterwards. The first sample will be taken immediately after the instillate solution is evacuated from the abdominal cavity. The second sample will be taken immediately after flushing. In the group of patients receiving HIPEC without flushing one 5-cm diameter non-tumour peritoneal tissue sample will be taken immediately after the instillate solution is evacuated from the abdominal cavity. Immediately after resection, all tissue samples will be touched to filter paper in order to remove excess surface fluid. The processing of the tissue will be performed according to the method described by Elias et al. The concentration in non-tumour peritoneal bathed tissue is a good reflection of tumour bathed tissue (9).

Peritoneal fluid samples

To determine the decrease in concentration of unbound platinum concentrations in the heated peritoneal instillate three different 5ml fluid samples will be collected at the following time points: 5 minutes after the start of the HIPEC procedure, 15 minutes after the start of the procedure and at the end of the HIPEC procedure. Based on the measurements in these samples it is possible to follow the decrease of unbound platinum concentrations in the heated peritoneal instillate. An additional 5ml fluid sample will be taken from the sodium chloride 0.9% flush solution at the end of flushing, to determine unbound platinum concentration in the flushing fluid.

Blood samples

A total of thirteen 10ml heparinised blood samples will be collected from each patient. Each sample will be centrifuged within 10 minutes after collection for 5 minutes (1,000 g, 4°C) to separate plasma. Unbound platinum will be obtained by centrifuging the plasma fraction through a 30 kDa cut-off ultrafiltrate filter for 15 minutes (1,000 g, 20°C). Unbound platinum from plasma is performed as soon as possible after blood collection, to prevent a decrease of Pt levels due to progressive *ex vivo* binding of Pt to plasma proteins and erythrocytes. The unbound platinum will be stored at -20°C until analysis. The first three blood samples will be taken at 10, 20 and 30 minutes after the start of HIPEC. The other ten samples will be taken at $\frac{1}{4}$, $\frac{1}{2}$, 1, 2, 4, 12, 24, 36, 48 and 72 hours after completion of the HIPEC procedure.

[figure not shown]
Total unbound platinum concentrations will be measured. The individual AUCs are calculated with a trapezoidal approach.

Wound exudate samples

After the HIPEC procedure in the majority of patients one or more drains will be placed. The wound exudate is collected in drainage bottles. Each bottle is changed after 24 hours. This is the moment that personnel can be exposed to contaminated wound exudate. Each drain will produce around 100ml on the first day. The total volume of wound exudate per drain will be measured. A 5 ml sample of wound exudate will be collected from every drain bottle to determine total and unbound platinum concentration. Platinum concentrations will be measured with AAS in The Cancer biology laboratory, Institut Universitaire du Cancer de Toulouse (IUCT) Oncopole.

Duration and setting of the study

The study takes place at Radboud University Medical Centre in Nijmegen, the Netherlands. The study is expected to start in November 2017 and is expected to be completed within 1 year after study initiation.

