4.2 Inclusion criteria

In order to be eligible to participate in this study, a subject must meet all of the following criteria:

- 1) Subjects must provide written informed consent prior to performance of study-specific procedures or assessments and must be willing to comply with treatment and follow-up.

Note: Informed consent may be obtained prior to start of the specified screening window.

Note: Procedures conducted as part of the subject's routine clinical management (e.g., blood count, imaging study) and obtained prior to signing of informed consent may be utilized for screening or baseline purposes.

- 2) Age ≥ 18 years
- 3) Confirmed diagnosis of preoperatively identified primary or recurrent peritoneal carcinomatosis (PC) of colorectal origin who are planned for HIPEC treatment with oxaliplatin according to routine clinical care

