4.3 Exclusion criteria

Patients who do not achieve a cytoreduction score of CC-0 will be excluded from the study.

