10.2.2 Secondary study parameter(s)

- To explore the difference in platinum wound exudate concentration between patients with and without flushing after completion of HIPEC: mean wound exudate concentrations will be calculated for both groups (flushing vs. non-flushing). An independent t-test will be performed to explore differences.
- To explore, quantify and describe the effect of flushing after HIPEC on systemic exposure of oxaliplatin: The mean AUCs of unbound platinum will be calculated. AUCs of flushing vs. no flushing will be compared by performing an independent t-test
- To explore, quantify and describe the effect of platinum concentration in instillate on tissue platinum exposure: Regression analysis will be performed to model the relationship
- To explore, quantify and describe the effect of the degree of cytoreduction on systemic unbound platinum exposure: Regression analysis will be performed to model the relationship
- To explore, quantify and describe the effect of platinum concentration in instillate on systemic unbound platinum exposure: Regression analysis will be performed to model the relationship

PK parameters for unbound platinum (AUC_{0-72h} , C_{max} and t_{max}) will be calculated by non-compartmental analysis. After finalizing the study the data will additionally be analyzed by Nonlinear mixed effect modeling to estimate the PK parameters for the population and the individual patients.

Based on the individual concentration-time data, the following PK parameters will be determined (non-compartmental analysis).

AUC_{0-72h} : the area under the unbound platinum concentration-time curve calculated (linear trapezoidal method) until the last measurable platinum concentration.

C_{max} : the maximum unbound platinum drug concentration

t_{max} : the time to reach maximum unbound platinum drug concentration.

Individual and mean unbound platinum concentrations will be presented. Overlay presentations will be given to illustrate intersubject variability. Descriptive statistics will be used to calculate the unbound platinum concentration at each sampling time.

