APPENDIX 3: Study procedures overview

Procedure	Flushing group				
	Screening	Time relative to the day of surgery			
	Day -14 until day 0	Day 0	Day 1	Day 2	Day 3
Written informed consent	X				
Inclusion/exclusion criteria	X				
Anamnesis/medical history	X				
Demography	X				
Concomitant Medications	X				
Laboratory clinical chemistry	X				
Cytoreduction and HIPEC with flushing afterwards ¹		X			
Blood PK sampling ²		X	X	X	X
Peritoneal PK sampling ³		X			
Tissue collection ⁴		X			
Wound exudates sampling ⁵		X	X	X	X

¹ flushing is performed with 2L/m² of sodium chloride 0.9% during 5 minutes

² blood samples (timepoints relative to the start of HIPEC): 10min, 20min, 30min, 45min, 1h, 1½ h, 2h, 4h, 12h, 24h, 36h, 48h, 72h.

³ peritoneal samples (timepoints relative to the start of HIPEC): oxaliplatin solution: 5min, 15min, 30min; flushing solution: 45min.

⁴ tissue samples of peritoneum: pre- and post-flushing

⁵ wound exudate samples will be taken each time a drain bottle is changes. Sampling continues until the drain is removed or until day 3 post-HIPEC has been reached.

Procedure	Non-flushing group				
	Screening	Time relative to the day of surgery			
	Day -14 until day 0	Day 0	Day 1	Day 2	Day 3
Written informed consent	X				
Inclusion/exclusion criteria	X				
Anamnesis/medical history	X				
Demography	X				
Concomitant Medications	X				
Laboratory clinical chemistry	X				
Cytoreduction and HIPEC without flushing afterwards ¹		X			
Blood PK sampling ²		X	X	X	X
Peritoneal PK sampling ³		X			
Tissue collection ⁴		X			
Wound exudates sampling ⁵		X	X	X	X

¹ no additional flushing is performed

² blood samples (timepoints relative to the start of HIPEC): 10min, 20min, 30min, 45min, 1h, 1½ h, 2h, 4h, 12h, 24h, 36h, 48h, 72h.

³ peritoneal samples (timepoints relative to the start of HIPEC): oxaliplatin solution: 5min, 15min, 30min

⁴ tissue sample of peritoneum after evacuation of oxaliplatin-solution

⁵ wound exudate samples will be taken each time a drain bottle is changes. Sampling continues until the drain is removed or until day 3 post-HIPEC has been reached.

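### No pre-HIPEC blood sample is planned, so platinum left from earlier treatment cannot be detected in, or subtracted from, the unbound-platinum AUC0-72h

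*Protocol*

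**What the plan says.** **Blood sampling.** Section 3 fixes the number of samples: "A total of thirteen 10ml heparinised blood samples will be collected from each patient". The first three come during perfusion: "The first three blood samples will be taken at 10, 20 and 30 minutes after the start of HIPEC". The remaining ten run from ¼ to 72 "hours after completion of the HIPEC procedure". Appendix 3 lists thirteen times for both groups, "10min, 20min, 30min, 45min, 1h, 1½ h, 2h, 4h, 12h, 24h, 36h, 48h, 72h". Table 1 in Section 8.3 marks no pharmacokinetic sample at baseline.

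**Tissue sampling.** Under Section 3, every peritoneal sample is taken after the instillate has been evacuated.

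**Who may enter.** Section 4.2 admits "Confirmed diagnosis of preoperatively identified primary or recurrent peritoneal carcinomatosis (PC) of colorectal origin". Section 4.3 has one exclusion: "Patients who do not achieve a cytoreduction score of CC-0 will be excluded from the study". Neither section mentions earlier platinum or a washout. Section 1 cites, for this disease, a median survival of "1 year with chemotherapy including oxaliplatin". Section 8.1.3 collects medical history and current medication at baseline, but does not ask for earlier platinum or its date.

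**Assay and analysis.** Section 10.1 names atomic absorption and ICP-MS, both of which quantify platinum. Plasma is ultrafiltered first (Section 3). Section 10.2.2 defines AUC0-72h for unbound platinum as the area "calculated (linear trapezoidal method) until the last measurable platinum concentration", with no baseline term. Group AUCs are compared by an independent t-test, and AUC is regressed on instillate concentration and on degree of cytoreduction.

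**The concern.** An assay for the element cannot tell platinum given weeks earlier from platinum given in this procedure. The usual safeguard is a sample before the dose. Here there is none, while patients with earlier systemic platinum may enter.

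Any background still in the ultrafiltrate is integrated over three days and credited to this HIPEC. The flushing and non-flushing groups are the first ten and the last ten patients (Section 8.2), so randomisation does not balance earlier treatment between them. A difference in earlier platinum could pass for part of a flushing effect on systemic exposure, and it would add noise to the AUC regressions. A later analysis plan cannot repair this, because a sample that was not collected cannot be subtracted.

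**Working it through.** **1. Sample count.** Three during perfusion plus ten afterwards is 13, the stated total. No pre-dose sample fits within it. Section 3, Table 1 and Appendix 3 agree on this, so Figure 1, which is not shown, is unlikely to add one.

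**2. Effect on AUC0-72h.** Let c be a constant unbound background.
- Added area ≈ 72 h × c.
- With c = f × Cmax, relative inflation = 72 × f ÷ (AUC/Cmax).
- The documents give neither f nor AUC/Cmax. Both are assumptions here.

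| Background f | AUC/Cmax = 3 h | 5 h | 10 h |
|---|---|---|---|
| 0 | 0% | 0% | 0% |
| 0.1% of Cmax | 2.4% | 1.4% | 0.7% |
| 1% of Cmax | 24% | 14% | 7% |

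For example, 72 × 0.01 ÷ 3 = 0.24.

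**3. Why the time-zero value matters.** Within the first trapezoid, using 0 in place of c at time zero changes the area by ½ × (10/60) h × c = 0.083 h × c. That is trivial beside 72 × c. The sample is needed as the measurement of background, much more than to complete the first ten minutes of the curve.

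**4. Upper limit from planned data.** A constant background cannot exceed the unbound level in the same patient's 48 h and 72 h samples. This caps c but does not estimate it, because those samples also contain platinum from the study dose.

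**5. Primary tissue endpoint.** Section 4.4 states n = 10 for a 25% difference, 20% intra-patient variability, 90% power and one-sided 0.05.
- On the log scale, SD of the paired difference = √2 × √ln(1.04) = 0.280 and the mean difference = −ln(0.75) = 0.288. The noncentral t gives n = 10, with 91.1% power. The stated figure is reproduced.
- Add a constant b to both readings: (pre + b) − (post + b) = pre − post. The t-test on ng/mg is unchanged.
- Simulation with 200,000 trials (n = 10, ratio 0.75, 20% CV on the HIPEC platinum, constant background making up 0, 10 or 20% of the pre-flush reading) gave about 91% power at all three levels, on both the raw and the log scale.
- The percentage change does shrink: measured fall = 25% × (1 − s), where s is the old share of the pre-flush reading. An assumed s of 10% gives 22.5%, and 20% gives 20%.

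**The case against.** **Ultrafiltration removes much of the old platinum.** This stands in part. The systemic endpoint is unbound platinum after a 30 kDa filter, so protein-bound and erythrocyte-bound residue does not reach the assay. Only what is still ultrafilterable counts, and that may be very little. The documents give no level, and the planned samples cannot show that it is negligible.

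**Evidence of earlier platinum is thin.** This also stands in part. The remark in Section 1 concerns survival, not the treatment history of candidates for this study. Appendix 1 directs recurrence after oxaliplatin HIPEC to mitomycin C, although its oxaliplatin checklist also lists recurrence after primary HIPEC as an indication. Those two statements need reconciling. Earlier systemic platinum is open in either case.

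**The affected analyses are exploratory, and the groups are not randomised anyway.** True. Section 4.4 sizes only the primary objective, and a time-0 sample removes one possible source of bias, not all of them. That limits the weight of the point without answering it.

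**A stronger reading a reader might infer: the primary endpoint loses power.** If the mean log difference is shrunk for 10% or 20% old platinum while its SD stays at 0.280, power appears to fall from 91% to 84% or 75%. That requires the full 20% CV to apply to the old platinum as well, which the protocol does not say. A constant added to both readings shrinks the log-scale spread along with the mean and cancels outright in ng/mg, the scale on which the endpoint is expressed. The documents do not support a loss of power.

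**Conclusion.** The point holds as a gap in sampling for the systemic endpoint. AUC0-72h has no measured time-zero value, and a background of ultrafilterable platinum from earlier treatment can be neither detected nor removed.

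The size is unknown. It ranges from nothing (zero baseline) through 0.7–2.4% of AUC (background 0.1% of Cmax) to 7–24% (1% of Cmax). This assumes a background constant over 72 h and an AUC/Cmax of 3 to 10 h, and it is capped by the patient's own late samples. Bias in the group comparison further requires that earlier platinum differs between the two consecutive groups.

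The primary paired test is not threatened. If the background is constant between the two tissue samples, it affects only the percentage read against 25%. This is a cheap improvement to the exploratory AUC analyses, not a fault that undermines the study.

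**What to change.** - Add one pre-HIPEC (time 0) blood sample from the central venous catheter already placed as routine care, in Section 3, Table 1 and Appendix 3, and change the stated total from 13 to 14.
- Use it as the first point of AUC0-72h, and report AUC with and without baseline correction as a sensitivity analysis.
- Record the date of the last platinum dose with the medical history in Section 8.1.3.
- Keep a tissue blank only if suitable non-tumour peritoneum is already in the cytoreduction specimen removed before HIPEC. The protocol does not say that it will be, so no extra excision should be built on this point.

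Cost: one further 10 ml draw and one further assay per patient (plus one assay where a tissue blank happens to be available). No added visit and no change to treatment.
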